5.5.8 Prohibited treatment

Patients who have met exclusion criteria for exclusionary medications will not be allowed to join the study. Once the patient has entered the study at Visit 3 and while the patient is on therapy, use of the following treatments are NOT allowed concomitantly with the study drug:

- Immunosuppressive medication (e.g. cyclosporine, azathioprine, methotrexate, cyclophosphamide, mitoxantrone, cladribine, rituximab, alemtuzumab);

- Other concomitant medications: immunoglobulins, monoclonal antibodies (including natalizumab), IFN β , glatiramer acetate, teriflunomide, dimethyl fumarate, adrenocorticotrophic hormone (ACTH).
- Class Ia (e.g. quinidine, disopyramide) or Class III (e.g. amiodarone, sotalol) anti-arrhythmics
- Heart-rate-lowering drugs (e.g.: Beta blockers); heart-rate lowering calcium channel blockers (e.g. verapamil, diltiazem or ivabradine)
- Digoxin, anticholinesteratic agents, pilocarpine

Careful planning is required if these medications are taken during the Core Phase (after the patient discontinued study drug treatment) then the patient must meet the washout exclusion criteria for these medications before entry into the Extension Phase. Washout of these medications must occur with adequate time to complete the full washout period prior to enrollment in the Extension Phase at Visit 15.

The administration of any live or live attenuated vaccine is prohibited while patients are receiving study drug and for 2 months after last dose of study drug.

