Subject classification in the analysis sets is entirely based on protocol deviation and non-protocol deviation criteria. A list of protocol deviations are specified prospectively in the Edit Check Specification. A subset of these protocol deviation criteria results in the exclusion of the subjects from analysis.

Table 3-1 provides a list of pre-defined protocol deviations considered important enough to lead to exclusion of a subject from an analysis set. These are taken from the Edit Check Specifications.

Table 3-1 Specifications of important protocol deviations

Deviation ID	Description of deviation	Excl. from analysis dataset				
		SCR	RAN	FAS	SAF	PPS
I01	Informed consent was not obtained. However, study assessments were performed.	X	X	X	X	X
E01	Patient has progressive multiple sclerosis. However, patient was randomized.			X		X
E04	Patient fulfills either the definition of ADEM or the criteria for neuromyelitis optica. However, patient was randomized.					X
E04A	Any patient is positive for aquaporin 4 at Screening. However, patient was randomized					X
E05B	Patient was treated with high dose intravenous immunoglobulin within 2 months prior to randomization. However, patient was randomized.					X

Deviation ID	Description of deviation	Excl. from analysis dataset				
		SCR	RAN	FAS	SAF	PPS
E05E	Any patient previously treated with excluded immunosuppressive or DMT medications within per protocol (Amend 4 or higher criteria) specified time windows at any time. However patient was randomized.					X
E05F	Patient has been previously treated with fingolimod at any time. However patient was randomized.					X
E26	Patient took study drug or therapy within 180 days or 5 half-lives of Randomization, whichever is longer. However, patient was randomized.					X
I03	Central MRI review completed and diagnosis of MS not confirmed. However, patient was randomized.			X		X
I04B	Number of relapses within: 1 yr prior to randomization is < 1, or 2 yrs prior to randomization is < 2; or 6 mths no Gd lesions. However patient was randomized.					X
I05	EDSS score at screening/baseline was greater than 5.5. However, patient was randomized.					X
M01	Patient used immunosuppressive medication during double blind treatment					X
O02 ¹	Site did not follow per protocol blinding procedures such that the integrity of the study may have been compromised.					X
O02A ¹	Sponsor provided potentially unblinding information to the site that could have compromised the integrity of the study.					X

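### The per-protocol exclusion for concomitant medication (M01) names only immunosuppressives, so a patient who adds a prohibited disease-modifying MS drug to continuing blinded treatment stays in the set

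*SAP*

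**What the plan says.** SAP 3.1 forms the PPS by removing from the full analysis set (FAS) patients with major deviations that could distort the FAS results. These deviations are set by pre-defined criteria before unblinding. The SAP leaves little room for case-by-case judgement: "Subject classification in the analysis sets is entirely based on protocol deviation and non-protocol deviation criteria". It adds: "Table 3-1 provides a list of pre-defined protocol deviations considered important enough to lead to exclusion of a subject from an analysis set".

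Three rows of Table 3-1 matter here:

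- M01, marked for the PPS only: "Patient used immunosuppressive medication during double blind treatment".
- E05E, on treatment before randomisation: "Any patient previously treated with excluded immunosuppressive or DMT medications".
- E05B, on high-dose intravenous immunoglobulin in the two months before randomisation.

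Protocol 5.5.8 states the on-study rule: "while the patient is on therapy, use of the following treatments are NOT allowed concomitantly with the study drug". Its first bullet begins "Immunosuppressive medication (e.g. cyclosporine, azathioprine, methotrexate" and goes on to name rituximab, alemtuzumab, cladribine and mitoxantrone, among others. Its second bullet begins "Other concomitant medications: immunoglobulins, monoclonal antibodies (including natalizumab" and continues with IFN beta, glatiramer acetate, teriflunomide, dimethyl fumarate and ACTH. Later bullets concern antiarrhythmic and heart-rate-lowering drugs and are not at issue here.

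**The concern.** A second disease-modifying drug acts directly on relapses and on new or enlarging T2 lesions. It is therefore among the clearest deviations that a per-protocol analysis should remove. The protocol prohibits such drugs on study and the SAP excludes patients for some of them before randomisation, yet the on-study row does not mention them.

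At stake are the supportive PPS analyses: confirmed relapses and all relapses (SAP 4.2.1.1), and the n/neT2 rate (SAP 4.2.2). If the PPS and the FAS keep the same affected patients, agreement between them says less about robustness than it appears to.

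M01 also has a timing problem in the other direction. It refers to double-blind treatment, and Protocol Table 6-2, the schedule for patients who have stopped study drug, carries a double-blind treatment heading too. Read literally, M01 could remove a patient for a drug begun only after study drug was stopped.

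**Working it through.** The point rests on wording, so the check is of every route by which such a patient could leave the PPS.

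**Step 1: all 19 rows of Table 3-1.**

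| Rows | Subject | Covers a DMT added on study? |
|---|---|---|
| M01 | Immunosuppressives on study | Not by its words |
| E05B, E05E, E05F, E26 | Treatment before randomisation | No |
| S03A, S05, S07, S12, S14 | Blinded study drug: compliance, kits, expiry, dose step, accountability | No |
| O02, O02A | Blinding | No |
| I01, I03, I04B, I05, E01, E04, E04A | Consent, diagnosis, eligibility | No |

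**Step 2: can M01 be read broadly?** E05E joins immunosuppressive and DMT with *or*, as two terms. Protocol 5.5.8 puts the two groups in separate bullets. Both favour the narrow reading. Drugs named in the first bullet of 5.5.8 are covered by M01; the gap is the second bullet.

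**Step 3: other routes.**

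- SAP 3.3 adds only patients whose treatment code was revealed.
- The general PPS definition depends on the pre-defined criteria, so it adds nothing beyond them.
- The PPS drops efficacy data after permanent discontinuation, which helps only if study drug is stopped. Protocol 5.5.9 lists prohibited medication among reasons that may support stopping, not among those that require it.

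**Step 4: the resulting inconsistency.** High-dose intravenous immunoglobulin six weeks before randomisation removes a patient; the same treatment during the study does not. A kit mismatch for more than 20% of the study removes a patient if the actual treatment differs from the randomised one (S05). Open-label IFN beta taken in the fingolimod arm does not.

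**Step 5: size, as illustration only.** The plan gives no figure on this point. The design rate ratio, 0.18/0.36 = 0.50, serves as the starting value. Assume that an added drug halves the relapse rate over a fraction *f* of one arm's PPS follow-up.

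- IFN arm only: ratio = 0.50/(1 − 0.5*f*)
- Fingolimod arm only: ratio = 0.50 × (1 − 0.5*f*)

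| *f* | IFN arm only | Fingolimod arm only |
|---|---|---|
| 5% | 0.50/0.975 = 0.513 | 0.50 × 0.975 = 0.4875 |
| 10% | 0.50/0.95 = 0.526 | 0.50 × 0.95 = 0.475 |
| 20% | 0.50/0.90 = 0.556 | 0.50 × 0.90 = 0.45 |

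Equal use in both arms cancels under this assumption.

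**The case against.** **The source specification is not available.** Table 3-1 is taken from the Edit Check Specifications, which may define M01 more broadly. The protocol also does not keep the terms fully apart: exclusion criterion 5 joins immunosuppressive and immunomodulatory medications, and 5.5.8 places two monoclonal antibodies under immunosuppressives. This stands as a limit. But neither document gives the broader definition, and if one exists the SAP row should state it.

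**Much is already handled.** Patients who stop study drug and then start another therapy have their later data cut. Concomitant medications are tabulated by arm (SAP 3.6.3), and so are protocol deviations (SAP 3.3). What remains is a drug added to continuing blinded treatment, at an unknown frequency. This narrows the point but does not remove it.

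**Excluding patients can itself bias.** If added drugs follow relapses, exclusion removes high relapsers. Suppose 5% of IFN patients are dropped, with observed rates 1.5 to 2 times the arm average and equal follow-up. The IFN rate becomes (1 − 0.05 × 1.5)/0.95 = 0.974 to (1 − 0.05 × 2)/0.95 = 0.947 of its value, and 0.50 again becomes 0.51-0.53. This is true of any per-protocol set. It argues for reading the PPS with care, not for an incomplete rule.

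**A stronger reading on direction.** A reader might infer that the PPS ratio must be pulled toward 1 because added drugs would be commoner in the arm with more relapses. That is plausible, but the documents give no usage by arm, and Step 5 shows that the bias can go either way.

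**A stronger reading on scope.** A reader might also infer that M01 is the only exclusion for any on-study medication problem. It is not: the five S-rows exclude for problems with the study drug itself.

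**Conclusion.** The gap holds on the text. M01 is the only concomitant-medication row, it names only immunosuppressives, and nothing else in the SAP or protocol removes a patient who adds a prohibited disease-modifying drug while staying on blinded treatment.

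Its size is unknown. Under the stated assumption of a halved rate over 5-20% of one arm's follow-up, the PPS rate ratio moves from 0.50 to a value between 0.45 and 0.56, depending on the arm. Only supportive analyses are affected. A reader might infer that the main result is in doubt; it is not, because the primary and key secondary tests use the FAS and their hierarchy does not depend on the PPS. Nor do the documents support dismissing FAS-PPS agreement altogether: it is weaker evidence in proportion to such use, which is unknown.

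The point is worth correcting before unblinding but is not critical. It rests on the narrow reading of M01, which the wording of E05E and 5.5.8 supports and the unavailable Edit Check Specifications could change.

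**What to change.** Before unblinding, align M01 with E05E and E05B, for example: *Use of immunosuppressive medication, of a disease-modifying MS drug prohibited by protocol 5.5.8, or of high-dose intravenous immunoglobulin, between first and last dose of study drug*, excluded from the PPS.

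- A drug started only after permanent discontinuation should not trigger M01, because those data are already cut.
- Immunoglobulin given as post-exposure prophylaxis should not trigger it. Protocol Appendix 3, section 15.5 foresees such use in patients taking study drug, while 5.5.8 lists immunoglobulins as prohibited without qualification. The sponsor must reconcile these two passages; this review takes no position on which should prevail.
- If disease-modifying drugs were left out on purpose, or the Edit Check Specifications already include them, the SAP should say so.

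The cost is one row of Table 3-1 and its edit check. The PPS may lose a few patients, and because the exclusion follows a post-randomisation event it can select patients, as in any per-protocol analysis. Reporting the number excluded under M01 by arm would let readers judge this.

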5.4 Treatment blinding

Core Phase:

This study will be conducted using a double-blind, double dummy design.

Patients randomized to one of the two treatment groups will be given the following medications:

Fingolimod Group: 0.25mg or 0.5 mg fingolimod capsule orally once daily +

IFN β -1a matching placebo i.m. injection once weekly

IFN β -1a Group: IFN β -1a 30 μ g i.m. injection once weekly +

fingolimod matching placebo capsule orally once daily

The study medication assignments will be blinded and will remain blinded for the entire double-blind Treatment Period and until the database lock for the Core Phase has been completed.

Patients, treating physician, site personnel, independent evaluating physician, First Dose Administrator and all Novartis personnel, involved in the study, with the exception of Novartis Drug Supply Management (DSM), Novartis on-line PK analyst, Novartis independent statistician and independent programmer for DMC, will remain blinded to the identity of the treatment from the time of randomization of the first patient until database lock. During this time period, the treatment codes will be accessible only to authorized personnel (those mentioned above and DMC members). The following measures will be taken to protect the blinding of the Independent Evaluating Physician (“rater”):

- Prohibited access of “rater” to patient records, laboratory data etc.
- Separate binders of worksheets and eCRF materials for “treating physician” and “rater”
- Prohibited cross-over of “treating physician” and “rater”
- Appropriate clothing for patients to cover potential injection sites during neurological examinations
- Limited interactions between evaluating physician and patients: permitting only a minimum required to perform the EDSS rating.

Fingolimod Extension Phase:

All patients in the Extension Phase will be treated with fingolimod, but the dose they received during the Core Phase (interferon or fingolimod) will remain blinded until the Core Phase database has been locked.

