8.3 Database management and quality control

Novartis staff review the data entered into the eCRFs by investigational staff for completeness and accuracy and instruct the site personnel to make any required corrections or additions. Queries are sent to the investigational site using an electronic data query. Designated investigator site staff is required to respond to the query and confirm or correct the data.

Concomitant medications entered into the database will be coded using the WHO Drug Reference List, which employs the Anatomical Therapeutic Chemical classification system. Medical history/current medical conditions and adverse events will be coded using the Medical dictionary for regulatory activities (MedDRA) terminology.

Laboratory samples will be processed centrally and the results will be sent electronically to Novartis (or a designated CRO).

ECG and CSSRS readings/values will be processed centrally and the results will be sent electronically to Novartis (or a designated CRO).

MRI scans will be processed centrally and the results will be sent electronically to Novartis.

Randomization codes and data about all study drug(s) dispensed to the patient and all IVR recorded dosage changes will be tracked using an Interactive Response Technology (IRT). The system will be supplied by a vendor, who will also manage the database. The database will be sent electronically to Novartis.

The occurrence of any protocol deviations will be determined. After these actions have been completed and the database has been declared to be complete and accurate, it will be locked and made available for data analysis. Any changes to the database after that time can only be made by joint written agreement between the Global Head of Clinical Information Sciences and the Clinical Franchise Head.

9 Data analysis

The statistical models specified in this section may be modified by including fewer covariates in the models in case the pre-specified models do not converge.

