9.1 Analysis sets

Core Phase:

All screened subjects (SCR): The SCR set comprises all subjects who were screened. The SCR will be used only for the summary of screening failures.

Randomized set (RAN): The RAN set comprises all subjects who were assigned a randomization number. The RAN will be used for the summaries of subject disposition, protocol deviation, demographic, baseline characteristics, and medical history data.

Full Analysis Set (FAS): The FAS comprises all randomized subjects with assigned treatments who took at least one dose of study medication. Subjects will be analyzed according to the randomized treatment assignment following the intention-to-treat principle, even if they actually received a different treatment. The FAS will be used for all efficacy analyses.

Per-protocol set: Consists of all patients in the full-analysis set who do not have any major protocol deviations that could confound the interpretation of analyses conducted on the FAS. Major protocol deviations will be determined according to the predefined protocol deviation criteria before treatment unblinding. Any efficacy data after study drug discontinuation will

be excluded. The per-protocol set will only be used for the supportive analyses of the primary efficacy variable.

Safety Set: The safety set includes all patients who received at least one dose of study medication. Subjects will be analyzed according to the actual treatment received. The Safety Set will be used for all safety analyses.

Fingolimod Extension Phase:

Extension Phase enrolled set: Includes all patients who were enrolled in the Extension Phase, whether or not they actually took any extension study medication. The Extension Phase enrolled set will be used for the summaries of subject disposition, protocol deviations, demographic, baseline characteristics, and medical history data.

Extension Phase FAS: All patients who *entered the Extension Phase* and received at least one dose of extension study medication. Patients will be analyzed according to the randomized treatment in the Core Phase. This analysis set will be used for all within-group efficacy analyses.

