3.1 Analysis sets

All screened subjects (SCR): The SCR set comprises all subjects who were screened. The SCR will be used only for the summary of screening failures.

Randomized set (RAN): The RAN set comprises all subjects who were assigned a randomization number. The RAN will be used for the summaries of subject disposition, protocol deviation, demographic, baseline characteristics, and medical history data.

Full Analysis Set (FAS): The FAS comprises all randomized subjects with assigned treatments who took at least one dose of study medication. Subjects will be analyzed according to the randomized treatment assignment following the intention-to-treat principle,

even if they actually received a different treatment. The FAS will be used for all efficacy analyses.

Safety Set (SAF): The safety set includes all subjects who received at least one dose of study medication. Subjects will be analyzed according to the actual treatment received. The Safety Set will be used for all safety analyses. Subjects will be analyzed according to the treatment they are assigned to at randomization unless a subject takes non-randomized study medications and does not take any study medication as randomized, in that case the subject will be analyzed according to the treatment actually taken.

Per-protocol set (PPS): The PPS is a subset of FAS, consists of all randomized subjects who take at least one dose of study medication and have no major protocol deviations that could confound the interpretation of analyses conducted on the FAS. Major protocol deviations will be determined according to the pre-defined protocol deviation criteria before treatment unblinding. For analyses performed on the PPS, any efficacy data assessed after permanent discontinuation of study medication will be excluded. The PPS will primarily be used for the supportive analyses of the primary efficacy variable and the key secondary variable.

Follow-up set (FUS): The FUS consists of all subjects in the safety set who have at least one visit or who have AE, MS relapse, or concomitant medication starting after study drug discontinuation, but before first dose of the extension study medication (if applicable). Subjects will be grouped in the same way as described above for the analysis on the safety set. Only the safety follow up data analysis will be performed on the follow-up set.

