S03A	Compliance less than 80 percent with study medication based on drug accountability log at site over entire study.					X
S05 ²	Incorrect study medication kit given and does not match assigned randomized number for more than 20% of study duration.					X
S07	expired study medication kit given for more than 20% of study duration					X
S12 ³	Patients body weight increases to >40 kg sustained over 2 scheduled visits (3 months apart) and dose is not increased to 0.5 mg for more than 90 days					X
S14	Monitoring of drug compliance was inconsistent or incomplete, resulting in an inadequate documentation for drug accountability					X

¹ Findings with strong evidence of potential unblinding in the data (e.g. blinding information that belongs to the blinded database but is reported in the main database) after DBL will be defined and added as new entries for PD O02 or PD O02A in VIOPTO and excluded from PPS analyses.

² Only exclude such PD from PPS if the actual treatment based on the kit numbers (available after DBL) does not match the randomized treatment.

³ Only exclude such PD from PPS if the patient was randomize to FTY arm.

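### A footnote to SAP Table 3-1 lets entries under deviation codes O02 and O02A be made after database lock on an undefined standard, against the rule that per-protocol exclusions are settled before unblinding

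*SAP*

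**What the plan says.** The SAP's general rule (section 3.1, definition of the PPS) is: "Major protocol deviations will be determined according to the pre-defined protocol deviation criteria before treatment unblinding". Protocol 9.1 has the same rule: "Major protocol deviations will be determined according to the predefined protocol deviation criteria before treatment unblinding". Protocol 8.3 gives the order of events. Deviations are determined, and then: "After these actions have been completed and the database has been declared to be complete and accurate, it will be locked". Protocol 5.4 says that sponsor and site staff, apart from a few named functions, "will remain blinded to the identity of the treatment from the time of randomization of the first patient until database lock".

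SAP Table 3-1 lists the deviations that remove a patient from an analysis set. O02 (the site did not follow the blinding procedures) and O02A (the sponsor sent the site potentially unblinding information) remove a patient from the PPS only. Footnote 1, attached to both, concerns "Findings with strong evidence of potential unblinding in the data". Its one example is information from the blinded database turning up in the main database. Such findings "after DBL will be defined and added as new entries for PD O02 or PD O02A in VIOPTO and excluded from PPS analyses".

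In the same table, M01 reads "Patient used immunosuppressive medication during double blind treatment". Protocol 5.5.8 lists immunosuppressants in one bullet. A separate bullet begins "Other concomitant medications: immunoglobulins, monoclonal antibodies (including natalizumab" and goes on to interferon beta, glatiramer acetate, teriflunomide and dimethyl fumarate.

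**The concern.** A per-protocol analysis is useful support only if its membership was fixed by people who could not know how each exclusion would move the result. Footnote 1 leaves part of that membership to a judgement made after lock. O02 and O02A are worded broadly, in terms of study integrity that may or could have been compromised, and the footnote adds only an example.

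The judgement may also fall unevenly by arm. The footnote does not say which data are meant, but lymphocyte counts are an obvious candidate. Protocol 1.1 says fingolimod reduces them to 20-30% of baseline, and protocol 6.5.4 and 15.4 withhold them from sites. A leaked low count points to an arm more strongly than a leaked normal one. If the strength of the evidence is judged from the value, the exclusions can follow treatment.

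At stake is the weight that can be put on the PPS repeats of the ARR analyses (SAP 4.2.1.1, Table 4-1) and of the key secondary analysis (Table 4-2).

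**Working it through.** The plan states no figure on this point, so the check is a comparison of text.

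1. **Timing.** Protocol 8.3 puts deviations before lock. Footnote 1 puts new O02 and O02A entries after lock. These cannot both be followed.
2. **Blinding.** Protocol 9.1 and SAP 3.1 require deviations to be determined before treatment unblinding. Protocol 5.4 keeps the blind until database lock and describes no blinded interval after it. Footnote 2 to the same table describes kit-based actual treatment as available after lock. The SAP therefore expects treatment information to be accessible in the period when footnote 1 operates.
3. **Criterion.** The general rule needs pre-defined criteria. The codes are pre-defined, since SAP 3.1 says the deviation list is specified prospectively. The threshold for an entry is not. Footnote 1 gives no operational definition, names no decision-maker and does not say that the decision is blinded.
4. **Comparison with the neighbouring rules.** Footnote 2 (kit mismatch) and footnote 3 (fingolimod arm only) also need treatment information, but each applies a fixed rule to a deviation already recorded. SAP 3.3 removes patients whose code was revealed, using a mark on the study completion form. Footnote 1 alone leaves open who is excluded.
5. **Reach.** Table 3-1 marks O02 and O02A for exclusion from the PPS only. SAP 4.2, 4.2.1 and Table 4-2 place the primary and key secondary tests on the FAS. The hierarchical procedure in SAP 4.2.2.1 uses only those two tests, so type I error is untouched.
6. **M01.** Protocol 5.5.8 separates immunosuppressants from the other MS therapies. M01 uses only the first term. E05E, the matching entry for prior treatment, names disease-modifying therapies as well. Read literally, concurrent use of a prohibited disease-modifying therapy does not trigger M01. Other provisions do not fully close the gap: protocol 5.5.9 lists prohibited medication among conditions that may support stopping study drug, and the PPS drops efficacy data only after permanent discontinuation.

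**The case against.** The strongest defence is practical. A leak from the blinded database into the main one may be detectable only when the two are compared, which may not be possible before lock. The footnote was written into the SAP in advance, and it does not say that treatment codes or relapse counts are consulted. Lock is also not the same act as release of codes: if the review fell between the two, the rule on unblinding could still be met. There is some transparency as well. SAP 3.3 tabulates deviations leading to PPS exclusion by treatment group, and protocol 8.3 requires joint written agreement of two senior sponsor roles for changes to the locked database (the documents do not say whether the deviation file is part of it).

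Much of this stands. It explains the timing and rules out three stronger readings:

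- A reader might infer that new kinds of deviation can be invented after lock. The footnote adds entries under existing codes.
- A reader might infer that exclusions will be chosen with codes and outcomes in view. The documents make that possible but do not state it.
- A reader might attach a size. Take the planning rates of 0.18 and 0.36, and assume 90% of the planned follow-up: 0.9 × 95 × 2 = 171 patient-years per arm, or 30.8 and 61.6 expected relapses. Removing three fingolimod patients (6 patient-years) who carry 4 relapses gives (26.78/165)/0.36 = 0.451; with 6 relapses, (24.78/165)/0.36 = 0.417. But three such patients are expected to carry 3 × 0.36 = 1.08 relapses, and removing that number leaves 0.500. With k = 0.82, their total is negative binomial with mean 1.08 and size 3/0.82; it reaches 4 with probability about 4%, and 6 about 0.5%. Removing three interferon patients with 4 to 6 relapses would move the ratio the other way, to 0.516-0.535. The shift depends on hand-picking patients, and nothing in the documents supports that.

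The defence does not supply a criterion, a blinded decision or a written interval between lock and release of codes. Even if the review took place in such an interval, the order in protocol 8.3 would still be broken.

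On M01, the term is undefined and the table is drawn from an Edit Check Specification that is not among these documents, so M01 may be applied more widely than it reads. That is a reason to word it clearly.

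**Conclusion.** The conflict is real and lies in the text. Footnote 1 permits O02 and O02A exclusions from the PPS after lock, on an undefined standard, whereas SAP 3.1, protocol 9.1 and protocol 8.3 require the opposite order and fixed criteria.

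Its reach is limited to the supportive PPS analyses of ARR and new/newly enlarged T2 lesions. The FAS tests and type I error are unaffected. It would go too far to say that robustness can no longer be judged, because the supportive FAS analyses of on-drug relapses and of all relapses do not depend on this footnote. No size of effect can be derived, since the documents do not say how many patients might be excluded, from which arm, or with how many relapses.

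The conclusion assumes that the footnote is applied as written and that no other document sets a blinded review between lock and code release. A separate procedure of that kind would settle the unblinding point, but the SAP should then refer to it and reconcile it with protocol 8.3.

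The M01 wording is a secondary and independent gap. It rests on a literal reading, and the documents give no frequency for concurrent use.

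**What to change.** Amend SAP 3.1 and footnote 1 as follows:

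- State what counts as evidence for an O02 or O02A entry, for example a specified type of blinded-database record present in the main database. Base it on the presence of the record and not on its value.
- Have existing staff who are still blinded apply the criterion, and document each decision.
- Freeze the PPS list before treatment codes are released. Do this before lock where possible. If the databases can be compared only after lock, write that interval into the SAP as an explicit exception to the order in protocol 8.3.
- If a leak is found after codes are released, keep the patient in the pre-specified PPS, list the finding, and show the PPS result with and without those patients as a labelled post hoc run.
- Reword M01 so that it covers concurrent use of the MS therapies that protocol 5.5.8 prohibits, in line with E05E.

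The cost is a few lines of SAP text, one documented check before code release, and at most one extra PPS run for each affected endpoint. No additional staff or data are needed.
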